### *Planned Sensitivity Analyses*

1. Best-Case Scenario for Missing Data
  - o Assume all patients with missing mortality data in the control group die on the date of last follow-up. Assume all patients with missing mortality data in the intervention group survive to one year.
2. Worst-Case Scenario for Missing Data
  - o Assume all patients with missing mortality data in the control group survive to one year. Assume all patients with missing mortality data in the intervention group die on the date of last follow-up.

### ***Hypothesis 2: Is EEG Guidance Intervention Associated with Improved Quality of Life One Year After Surgery?***

*Patient Population:* Patients randomized to intervention or control (N = 1232)

*Primary Predictor Variable:* EEG guidance intervention

(X=0 for control or X=1 for intervention)

Intention to treat

*Outcomes:* Veterans RAND 12-Item Health Survey (VR-12) physical component score (PCS), VR-12 mental component score (MCS), one year postoperatively

- Partially completed VR-12 surveys will not be scored and will be considered missing.

*Data Description Plan:* Box plots of VR-12 PCS and MCS at baseline, 30 days, and 1 year for the two groups. Provide median, interquartile range, and range at each time point.

*Analysis Plan:* Generalized linear model

$$y_{365} = \beta_0 + f(y_0) + \beta_1 x + \beta Z + \varepsilon$$

- In this equation,  $y_{365}$  is the quality of life (either VR-12 PCS or VR-12 MCS) at one year, and  $y_0$  is the quality of life metric at baseline.  $x$  is the EEG guidance intervention ( $x=0$  for control or  $x=1$  for intervention).  $Z$  is a vector of additional variables for which we will adjust.
- $f(y_0)$  is a potentially nonlinear function describing the relationship between baseline quality of life and quality of life at one year. This function will be modeled using splines.
- Will perform unadjusted ( $Z = \text{null}$ ) and adjusted ( $Z$  not null) analyses. Will adjust for age, sex, American Society of Anesthesiologists (ASA) physical status classification (1-2 vs 3 vs 4-5), number of comorbid conditions, baseline poor functional capacity (<4 METS), history of falls (yes/no within previous 6 months), evidence of abnormal cognition (preoperative Short Blessed Test score > 4), surgery type (cardiac versus non-cardiac), length of anesthesia (Anesthesia Stop – Anesthesia Start)
  - o Multiple imputation may be performed to address missing values of these variables
- Any patient with missing quality of life either at baseline or at one year will be excluded.
- $H_0: \beta_1 = 0$  (The null hypothesis is that the EEG guidance intervention has no association with postoperative quality of life.)

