#### *Planned Sensitivity Analyses*

##### 1. Best-Likely-Case Scenario for Missing Data

- o For patients missing baseline quality of life, set the baseline quality of life equal to the mean baseline value for the appropriate stratum of the population. Population to be stratified based on type of surgery (cardiac versus non-cardiac) and history of falls.
- o For patients in the intervention group missing one-year quality of life, set the quality of life value equal to the maximum postoperative quality of life within the patient's stratum (still stratified by type of surgery and history of falls).
- o For patients in the control group missing one-year quality of life, set the quality of life value equal to the minimum postoperative quality of life within the patient's stratum (still stratified by type of surgery and history of falls).
- o Patients who die before one year will be excluded.

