##### 2. Worst-Likely-Case Scenario for Missing Data

- o For patients missing baseline quality of life, set the baseline quality of life equal to the mean baseline value for the appropriate stratum of the population. Population to be stratified based on type of surgery (cardiac versus non-cardiac) and history of falls.
- o For patients in the control group missing one-year quality of life, set the quality of life value equal to the maximum postoperative quality of life within the patient's stratum (still stratified by type of surgery and history of falls).

- For patients in the intervention group missing one-year quality of life, set the quality of life value equal to the minimum postoperative quality of life within the patient's stratum (still stratified by type of surgery and history of falls).
- Patients who die before one year will be excluded.

3. Expanded Control Group with Matched Cohort

- Each patient randomized in the ENGAGES trial will be matched to a patient enrolled in the SATISFY-SOS study.
  - All patients enrolled in SATISFY-SOS who meet the following criteria will be considered.
    - Age 60 or older
    - Hospital stay  $\geq$  2 days
    - Surgery between January 2015 and May 2018 (same dates as ENGAGES)
  - For each patient meeting the above criteria, a propensity score for enrollment in the ENGAGES trial will be constructed using logistic regression. Covariates included in the model will include age, sex, ASA physical status, surgery type (cardiac versus non-cardiac), and history of falls.
  - (Because all patients enrolled in ENGAGES were co-enrolled in SATISFY-SOS, the population described above will include all patients who were enrolled in ENGAGES.)
  - Patients enrolled in ENGAGES will be matched 1:1 without replacement to SATISFY-SOS patients not enrolled in ENGAGES based on the logit of the propensity score. A greedy nearest-neighbor algorithm will be used, with a maximum caliper width of  $0.2 * \text{the standard deviation in the logit of the propensity score}$ .
  - Use the same model structure described above.
  - Add a variable to Z indicating whether the patient was enrolled in ENGAGES.

4. Patient-Reported Subjective Quality of Life Change

- Analysis to include the subset of patients enrolled in ENGAGES who returned the SATISFY-SOS survey at one year
  - The survey includes a question asking if quality of life is better, the same, or worse compared to before surgery

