***Hypothesis 3: Is EEG Guidance Intervention Associated with Fewer Falls One Year After Surgery?***

*Patient Population:* Patients randomized to intervention or control (N = 1232)

*Primary Predictor Variable:* EEG guidance intervention

(X=0 for control or X=1 for intervention)

Intention to treat

*Outcomes:* Presence or absence of fall(s) during the one-year postoperative follow-up period, measured via patient report one the one-year ENGAGES survey

- Patients who did not fill out the survey (including both living non-respondents and deceased patients) will be excluded

*Data Description Plan:* Confusion matrix of falls versus EEG guidance intervention

*Analysis Plan:* Logistic regression

- Will perform unadjusted and adjusted analyses
- Will adjust for age, sex, American Society of Anesthesiologists (ASA) physical status classification (1-3 vs 4-5), number of comorbid conditions, history of falls (yes/no within previous 6 months), evidence of abnormal cognition (preoperative Short Blessed Test score > 4), surgery type (cardiac versus non-cardiac), length of anesthesia (Anesthesia Stop – Anesthesia Start)
  - o Note that ASA is dichotomized in this analysis, and functional capacity <4 METS has been dropped. These changes were made to reduce the number of degrees of freedom in the model, with the goal of having one degree of freedom per 10 patients who fell.
  - o Multiple imputation may be used to address missing values of these variables

*Planned Sensitivity Analyses*

1. Deceased Patients
  - o Assume all patients who die within one year have fallen.
2. Best-Case Scenario for Missing Data
  - o Assume all patients who die within one year have fallen.
  - o Assume that living patients in the intervention group with missing fall outcome data have not fallen. Assume that living patients in the control group with missing fall outcome data have fallen.
3. Worst-Case Scenario for Missing Data
  - a. Assume all patients who die within one year have fallen.
  - b. Assume that living patients in the intervention group with missing fall outcome data have fallen. Assume that living patients in the control group with missing fall outcome data have not fallen.
4. Expanded Control Group with Matched Cohort
  - o Use the same matched cohort as described above in Hypothesis 2.
  - o Perform a logistic regression as described above, also adjusting for whether the patient was enrolled in ENGAGES.
5. Number of Falls

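### One-year quality of life has no missing-at-random analysis that uses the 30-day VR-12, and the best/worst-case falls rules can code a patient with a reported postoperative fall as not fallen (minor)

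*SAP*

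**What the plan says.** **Quality of life (SAP, Hypothesis 2).** The main model regresses the one-year PCS or MCS on arm, a spline of the baseline score and, in the adjusted version, covariates. On missing scores: "Any patient with missing quality of life either at baseline or at one year will be excluded". In addition, "Partially completed VR-12 surveys will not be scored and will be considered missing". Imputation is optional and is attached to the adjustment covariates: "Multiple imputation may be performed to address missing values of these variables". The 30-day VR-12 enters only the box plots and summary statistics.

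The best- and worst-likely-case analyses give missing one-year scores the stratum maximum in one arm and the stratum minimum in the other. For a missing baseline they "set the baseline quality of life equal to the mean baseline value for the appropriate stratum of the population". On deaths, "Patients who die before one year will be excluded". The other two sensitivity analyses (matched cohort; better/same/worse question) do not deal with missing VR-12 scores. The protocol's random-effects model (Statistical Analyses, ii) uses baseline and 12 months only, so it does not use the 30-day score either.

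**Falls (SAP, Hypothesis 3).** The outcome is "Presence or absence of fall(s) during the one-year postoperative follow-up period, measured via patient report one the one-year ENGAGES survey". Patients who did not complete that survey are excluded from the main analysis. The best case says "Assume that living patients in the intervention group with missing fall outcome data have not fallen" and the worst case says "Assume that living patients in the control group with missing fall outcome data have not fallen". Neither makes an exception for a fall reported elsewhere. Yet the protocol (Outcome Measures, iii) asks about falls at 30 days as well as one year, and the SAP's Number of Falls analysis draws on a separate SATISFY-SOS one-year survey.

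**The concern.** For quality of life, the reader is offered complete-case or deliberately extreme bounds, with nothing between. The 30-day score is an early post-surgical measure of the same outcome and may be available for many one-year non-respondents. It could recover some precision, and it could show whether the result holds when response depends on early recovery. The main model also discards patients who have a one-year score but no baseline, although the SAP already defines a fill for them and uses it only in the bounds.

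For falls, the outcome is any fall in the year. A fall reported at 30 days, or on the SATISFY-SOS one-year survey, already settles it. A rule that codes such a patient as not fallen gives a bound that contradicts data in hand.

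**Working it through.** **1. The plan's own figure.** The protocol (Sample Size Calculations, ii) gives a 0.5-point difference, SD 2.5 for change, N = 1,000, two-sided 0.05, power above 80%. With d = 0.5/2.5 = 0.2 and 500 per arm, power is 88.5%. The statement holds.

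**2. Numbers missing.** One-year completion is assumed to be 80% (Sample Size Calculations) and was about 66% in the wider SATISFY-SOS cohort (Strengths and Limitations). Non-completers: 0.20 × 1,232 = 246; 0.34 × 1,232 = 419. Assume 5% die and that deaths count among non-completers (the protocol does not say whether its 66% counts them). Living non-respondents are then 15% (185) or 29% (357); with 2-10% deaths, 123-222 or 296-394. Responders are 986 or 813 of 1,170 survivors.

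**3. Power of the planned model.** With baseline correlation r and equal SDs, the residual SD is 2.5 × √((1+r)/2). At r = 0.6 (assumed), d = 0.2/√0.8 = 0.224, and power is about 94% at N = 986 and 89% at N = 813. Over r = 0.3-0.7 it is about 93-97% and 87-94%. At r = 0.6, power falls to 80% only near N = 630.

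**4. Keeping patients with no baseline.** Let share b of responders lack a baseline, with r = 0.6 so that 1 − r² = 0.64. Complete-case N is n(1 − b). With mean fill plus a missing indicator, effective N is n × 0.64/[0.64(1 − b) + b].

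| n | b (assumed) | Complete-case | With fill |
|---|---|---|---|
| 813 | 2% | 797 | 804 |
| 813 | 5% | 772 | 791 |
| 813 | 10% | 732 | 770 |
| 986 | 5% | 937 | 959 |

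At b = 5% the standard error falls by 1 − √(772/791) = 1.2%.

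**5. Adding the 30-day score.** With g = response among survivors (0.80/0.95 = 0.842, or 0.66/0.95 = 0.695), c = residual correlation of 30-day with one-year score (assumed 0.3-0.7), and a = share of living non-respondents with a 30-day score:

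effective N = 1,170 / [(1 − c²)/g + c²/(g + (1 − g)a)]

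For a, the protocol gives two targets: above 90% 30-day follow-up (Strengths and Limitations) and above 80% for 30-day patient-reported data in the pilot (Study Subjects). With 30-day rate t and one-year rate f, at least (t − f)/(1 − f) of non-completers answered at 30 days. That is 50% (f = 0.80) or 71% (f = 0.66) at t = 0.90, and 0% or 41% at t = 0.80. These floors include deaths and partly completed surveys, so I use a = 0-0.9.

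- 80% response: effective N goes from 986 to between 986 and 1,061; SE falls by 0 to 1 − √(986/1,061) = 3.6%.
- 66% response: from 813 to between 813 and 944; SE falls by 0 to 1 − √(813/944) = 7.2%.

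**6. Bias under a null effect (simulation, assumed response models).** If response depends on the 30-day score equally in both arms, complete-case bias is at most 0.003 SD. If the odds ratio per SD is 1.28 in one arm and 1.65 in the other, it is 0.01-0.03 SD. With a much stronger assumed contrast (log-odds slope 0.8 in control against 0-0.2 in intervention), it is 0.08-0.43 points, or 0.03-0.17 SD. Imputation with the 30-day score brings it close to zero in each case.

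**7. How wide the quality-of-life bounds are.** If a stratum spans 5-6 SD (assumed), the bounds shift the arm difference by (1 − 0.842) × 5 = 0.8 SD up to (1 − 0.695) × 6 = 1.8 SD. The design effect is about 0.2 SD.

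**8. Falls overwritten.** The 30-day fall risk under a constant hazard is 1 − 0.60^(1/12) = 4.2% from the protocol's assumed 40% per year, or 1 − 0.67^(1/6) = 6.5% from its cited 33% in six months. Known fallers per affected arm = 616 × living missing share × risk × a.

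- 80% response: 0 to 616 × 0.15 × 0.065 × 0.9 = 5, or 0-0.9 points.
- 66% response: 0 to 616 × 0.29 × 0.065 × 0.9 = 10, or 0-1.7 points.

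Patients who reported a fall on SATISFY-SOS but returned no ENGAGES survey would add to these counts. Their number is not in the documents.

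**The case against.** Complete-case regression on arm, baseline and covariates is itself valid when response depends only on those variables. A reader might infer that the main quality-of-life estimate is biased. The documents do not support that: material bias needs response to depend on early recovery differently by arm, no passage shows this, and patients, families and postoperative assessors are blinded (Randomization and Blinding). A reader might also infer a power shortfall; step 3 rules it out, and planned telephone follow-up makes 66% a pessimistic case.

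On baselines, the SAP already fills missing values in both bounding analyses, and nothing suggests that they are often missing. That limits the gain, but it does not explain why the main model drops these patients.

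On falls, the miscoding runs in the conservative direction. It lowers intervention risk in the best case and control risk in the worst case, so it can only widen the bounds, by at most about 6% (0.065 × 0.9) of one arm's living-missing share. A reader might infer that the main falls analysis is also miscoded; it is not, because it excludes these patients. Nor are the SATISFY-SOS one-year falls answers ignored: the Number of Falls analysis uses them without requiring the ENGAGES survey.

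What remains is a free gain in precision, a missing robustness check, and a falls rule that is wrong as written for a few patients.

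**Conclusion.** The point holds and is minor. No printed figure is wrong. For quality of life, the plan lacks a missing-at-random analysis that uses the 30-day VR-12, and it drops patients with a missing baseline without need. The benefit of changing this is modest precision (SE about 0-4% smaller at 80% response, 0-7% at 66%) plus a check on dependence of response on early recovery. For falls, about 0-5 patients per affected arm at 80% response, or 0-10 at 66%, could be coded against their own 30-day report, moving a bound by 0-1.7 points.

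All these sizes rest on assumptions: 5% deaths, residual correlation 0.3-0.7, 30-day coverage of living non-respondents 0-90%, and a constant fall hazard. If the 30-day rate only just meets the pilot's 80% target and one-year response is also 80%, both the imputation gain and the 30-day faller count could be close to zero.

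**What to change.** 1. Keep patients with a missing preoperative VR-12 in the main quality-of-life model, using the stratum-mean fill the SAP already defines plus a missing-baseline indicator. Allocation is revealed only in the operating room, so this missingness cannot depend on arm and the change adds no bias.
2. Beside complete-case, report a multiple-imputation analysis of one-year PCS and MCS for non-respondents not known to have died, using arm, strata, covariates, baseline and 30-day VR-12. Keep the existing bounds as the missing-not-at-random check.
3. Before applying the best- and worst-case falls rules, code as fallen anyone who reported a postoperative fall at 30 days or on the SATISFY-SOS one-year survey. This narrows both bounds slightly. Do not add only these known fallers to the main analysis, because that would inflate incidence.

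The cost is SAP wording and some programming, with no new data. The imputation brings a missing-at-random assumption, which should be stated with the result.

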We will follow the intention-to-treat principle for all analyses. The primary endpoint of our analysis is the incidence of postoperative delirium as defined previously. The incidence of delirium will be compared between groups using a chi-square test, and the difference in delirium incidence with 95% confidence intervals will be calculated. Prespecified exploratory subgroup analyses: we will test for effect modification by known baseline delirium risk factors (i.e., age [<70 and ≥ 70], sex, history of falls, and type of surgery [cardiac versus non-cardiac]).

ii) Effectiveness of EEG-guided anesthesia protocol in improving patient reported outcomes of health-related quality of life and preventing postoperative falls (Aim 2 in Figure 2)

Health-related quality of life

Random effects regression models based on PROC MIXED in SAS will be used to compare Physical Summary Score change over 12 months between the intervention and usual care group by introducing terms for time, indicator variables for treatment group and time x treatment group interactions with the latter set of regression coefficients of primary interest. The model will be controlled for baseline health-related quality of life. Potential confounding factors including age, gender and relevant comorbidities will be evaluated and controlled for in the model. We will utilize the same analysis approach to evaluate the Mental Summary Scores.

The analysis is primarily based on the following model: $Y_{it} = \alpha + \beta_1 t + \beta_{2A} X_{i1} + \beta_{3A} X_{i1}t + \beta_4 Y_{i0} + e_{it}$ (1) where Y_{it} = QOL for subject i at time t , where $t = 0$ for baseline, $t = 1$ for 12 months. $X_{i1} = 1$ if i th subject is in the Intervention group, = 0 otherwise $e_{it} \sim N(0, \sigma^2)$ β_{3A} is the mean difference in Physical Summary Score change between the Intervention and usual care groups. The coefficient β_{2A} allows for mean differences in Physical Summary Scores between groups at baseline. The coefficient β_4 allows the change in Physical Summary Score to depend on initial level.

Postoperative falls

Chi square test will be used to compare the incidence of falls at 12-months postoperatively between patients in the EEG-guided and in the usual care groups.

iii) Explore whether a multi-component safety intervention is associated with improved patient reported health-related quality of life and decreased incidence of postoperative falls (Aim 3 in Figure 2)

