Our sample size calculations are based on the anticipated delirium incidence and effect size for our primary endpoint analysis. Based on results of a previously published meta-analysis of four studies investigating the use of BIS-guided anesthetic administration, we conservatively assume an incidence of postoperative delirium in the routine anesthesia care group of 25%.²⁹ We performed a sample size sensitivity analysis and calculated different scenarios with different values for the delirium incidence in the intervention arm and corresponding power (80%, 90%, and 95%). With a two sided alpha $<5\%$ and 1,232 patients (616 per arm), the trial will have $>95\%$ power to detect an absolute decrease in delirium incidence $\geq 9\%$, $>90\%$ power to detect a decrease in delirium incidence $\geq 8\%$, and $>80\%$ power to detect a decrease in delirium incidence $\geq 7\%$. With a 7% decrease in delirium incidence, the 95% confidence interval would be approximately 3% to 12%. Even a 3% decrease in delirium incidence would be clinically important, suggesting that delirium would be prevented in one out of every 33 at risk patients who received EEG-guidance of general anesthesia.

ii) Health Related Quality of Life

The overall sample size of our study is defined through estimations of the primary outcome (delirium). For secondary analyses, we assume that ~80% of our trial population (~1,000 participants) will have completed the trial and the 1-year follow-up survey. With this sample size of 1,000, we can detect a difference of 0.5 points (standard deviation of 2.5) in the mean change of Physical Health Score from baseline to 1 year between the intervention and usual care group with a power of $>80\%$ and a two-sided alpha level of $p<0.05$.

iii) Postoperative Falls

This calculation is similarly based on the assumption that ~80% of our trial population (~1,000 participants) will have completed the trial and the 1-year follow-up survey. Based on a study that showed a preoperative fall prevalence of 33% over six months preoperatively in a similar patient population to the ENGAGES trial, we will conservatively assume an incidence of postoperative falls at 1-year in the routine anesthesia care group of 40%.¹¹⁰ With a sample size of 1,000, we will have $>80\%$ power to detect an absolute risk reduction of 12% between the EEG-guided and the usual care group at a two-sided alpha level of $p<0.05$.

Analysis of Pragmatic Elements of the ENGAGES Study

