The following limitations should be considered. A single clinical trial should seldom be regarded as definitive. As there is no clear estimate for the prior probability that EEG guidance of anesthesia prevents postoperative delirium, if the results of this trial do suggest that EEG-guidance of anesthesia might decrease delirium at the arbitrary statistical threshold of $p < 0.05$, it will be necessary to replicate this finding in future studies. On the other hand, even if the study finds a non-significant (at the arbitrary threshold of $p > 0.05$) decrease in delirium in the EEG-guided group, it is likely that follow-up studies will be warranted to clarify whether or not there is a clinically meaningful reduction in delirium with EEG-guidance of anesthesia, and whether there are specific patient populations that might especially benefit from this intervention. If EEG-guidance of anesthesia can prevent postoperative delirium, demonstrating its effectiveness will depend on clinicians' adherence to the protocol. However, the inability to blind clinicians to the trial allocation group is a potential source of bias and confounding. We are attempting to confirm that clinicians do alter anesthetic management based on the intervention during the pilot phase of the study. The inclusion of patients in a clinical trial focused on the prevention of delirium, and the provision of practical educational information to patients and family members could decrease the incidence of postoperative delirium. Furthermore, if the multi-component intervention is successful in preventing falls and in improving quality of life, this could curtail our ability to detect an impact of the EEG-guided anesthetic protocol on these outcomes. In addition to the pragmatic structured chart review, there are two clinical assessment methods that will be used to diagnose delirium: the CAM-ICU and the CAM. The CAM-ICU is less sensitive than the CAM, but is the only instrument that has been validated for patients who are non-verbal (i.e., with a breathing tube or tracheostomy in place). Based on our institutional data, the vast majority of patients enrolled in the study will be extubated within the first two postoperative days. Therefore, most patients will have delirium assessments with the CAM, which is the more sensitive and specific instrument. We will also test whether intubation status modifies the result in secondary analysis. The study design includes a 30-day and a 1-year follow up for patient reported outcomes, and incomplete follow-up is therefore a potential limitation. Based on our previous B-Unaware and BAG-RECALL studies,^{40,41} we are confident that we can achieve a 30-day follow up rate of >90%. In our SATISFY-SOS cohort, the 1-year follow up has yielded approximately 66% response rate. We have performed sensitivity analysis in our power calculations and have taken into account this potential attrition in our methods. Furthermore, we plan to enhance follow-up by using supplementary phone calls from members of the study team. As delirium is a fluctuating disorder, there is a risk that it can be missed by periodic assessments. We are attempting to mitigate this by assessing patients for delirium during a time of day (afternoon/evening) when delirium occurs more commonly. Furthermore, we are incorporating structured chart review, which has been validated as a complementary approach that increases the detection of delirium.^{93,94}

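### The main one-year VR-12 model drops patients with an observed one-year score because the baseline score is missing: an avoidable, probably small loss of precision

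*SAP*

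**What the plan says.** SAP, Hypothesis 2, takes all 1,232 randomised patients as its population, under intention to treat. The protocol (Statistical Analyses) states the same principle: "We will follow the intention-to-treat principle for all analyses".

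The SAP model regresses the one-year score on arm, a spline in the baseline score f(y0), and further covariates Z. Four statements bear on a missing baseline:

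- Main model: "Any patient with missing quality of life either at baseline or at one year will be excluded".
- Scoring: "Partially completed VR-12 surveys will not be scored and will be considered missing". One skipped baseline item is enough to make the baseline missing.
- Covariates: "Multiple imputation may be performed to address missing values of these variables". This stands under the list for Z, which does not include baseline VR-12.
- Sensitivity analyses 1 and 2 (best-likely and worst-likely case): "For patients missing baseline quality of life, set the baseline quality of life equal to the mean baseline value for the appropriate stratum", with strata formed by surgery type and falls history.

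The SAP gives no reason for treating the baseline score differently from Z, or for treating it differently in the main model and in these two sensitivity analyses.

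**The concern.** A patient with no ASA class but an observed one-year VR-12 may stay in the main analysis through imputation. A patient with no baseline VR-12 and the same observed outcome may not. Because f(y0) is in the model even when Z is empty, the rule also reaches the analysis labelled unadjusted. Sensitivity analysis 3 and exploratory analyses 2, 5 and 8 reuse the model structure and may inherit it.

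Two things are at stake. The first is precision: observed outcomes are discarded although the SAP already contains tools that would keep them. The second is smaller. Sensitivity analyses 1 and 2 are meant to show how far missing one-year scores could move the result, but they change the baseline rule and the outcome fill at the same time.

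**Working it through.** **Inputs from the documents.** 1,232 randomised, 1:1. For one-year follow-up the protocol's sample size section says "we assume that ~80% of our trial population (~1,000 participants) will have completed the trial and the 1-year follow-up survey"; 0.80 × 1,232 = 986. Its limitations section says of the source cohort that "the 1-year follow up has yielded approximately 66% response rate"; 0.66 × 1,232 = 813. The planning difference is 0.5 points with SD 2.5, two-sided alpha 0.05.

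**Inputs assumed.** The fraction m of responders with a missing baseline (2% to 20%), and the correlation ρ between baseline and one-year score (0.4 to 0.7). The documents give neither.

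**The plan's own figure.** With 500 per arm, SE = 2.5 × √(2/500) = 0.158, and 0.5/0.158 − 1.96 = 1.20, so power is 88.5%. This agrees with the stated power above 80%. Power of 80% needs 393 per arm, 786 in total.

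**Power under the exclusion rule.** The bottom row counts every kept patient as if the baseline were observed, so it is an upper bound.

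| Baseline missing | 1,000 one-year scores | 813 one-year scores |
|---|---|---|
| 2% | 87.9% | 80.6% |
| 5% | 86.9% | 79.4% |
| 10% | 85.1% | 77.2% |
| 20% | 80.7% | 72.3% |
| none lost | 88.5% | 81.4% |

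With 813 scores, power passes below 80% at 1 − 786/813, about 3% missing.

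**Variance of the arm effect relative to exclusion.** A patient with a baseline contributes information proportional to 1/(1 − ρ²); one without contributes proportional to 1. Efficient use of both gives the ratio

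(1 − m) / [(1 − m) + m(1 − ρ²)].

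- m = 2%: 0.98/0.9968 = 0.983 at ρ = 0.4 and 0.98/0.9902 = 0.990 at ρ = 0.7. The SE changes by less than 1%.
- m = 5%: 0.96 to 0.97.
- m = 10%: 0.90/0.984 = 0.915 at ρ = 0.4 and 0.90/0.951 = 0.946 at ρ = 0.7.
- m = 20%: 0.83 to 0.89.

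The equivalent number of extra responders is 986 × m × (1 − ρ²). At 10% this is 98.6 × 0.84 = 83 down to 98.6 × 0.51 = 50. Multiple imputation comes close to these values.

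**Stratum mean plus a missing indicator.** The ratio is

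[(1 − m)(1 − ρ²) + m] × (1 − m)/(1 − ρ²).

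At m = 10% it is 0.856 × 0.90/0.84 = 0.917 at ρ = 0.4, but 0.559 × 0.90/0.51 = 0.986 at ρ = 0.7, or about 80 down to 12 extra responders from the 887 left by exclusion. It reaches 1 when 1 − ρ² = (1 − m)/(2 − m) = 0.9/1.9 = 0.474, that is at ρ of about 0.72 to 0.73. Above that it is worse than exclusion.

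**Bias.** In simulation with 1,000 patients and 10% of baselines missing, at random or depending on the baseline value, exclusion and stratum-mean fill were both within 0.0013 SD of the true effect. A second simulation let one-year response depend on arm and baseline together (about 80% response, an assumed log-odds slope of ±0.5 by arm). Stratum-mean fill was then off by about 0.01 SD at 10% missing and 0.02 to 0.03 SD at 20%. Exclusion stayed within 0.004 SD.

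**The case against.** Sensitivity analyses exist to differ from the main analysis, and a complete-case main model with single imputation behind it is a common structure. The SAP states each rule plainly. A reader might infer that it contradicts itself; it does not.

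A reader might also infer that the main comparison is biased, or that filling the baseline is safe because it was measured before randomisation. The documents support neither. No bias from exclusion was found. The safety argument holds for the full randomised set, but the model is fitted to responders, who are selected after randomisation. There, exclusion still adjusts for an arm difference in baseline, and stratum-mean fill does not for the filled patients. This counts against mean fill as the remedy.

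The intention-to-treat argument is thin. Missing one-year scores remove 1,232 − 986 = 246 patients at 80% response, or 1,232 − 813 = 419 at 66%, and they stay out under any baseline rule. The attribution argument is also modest: if neither baseline rule biases the contrast materially, a systematic shift in sensitivity analyses 1 and 2 should come mainly from the extreme outcome values.

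Finally, VR-12 is listed among routinely acquired data and is assessed preoperatively in a cohort to which every participant belongs, so a low missing rate is plausible. All of this stands. It lowers the weight of the point but gives no reason to discard observed outcomes.

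**Conclusion.** The point holds as a minor one. The main model gives up observed one-year scores that the SAP's own imputation provision could keep, at a cost in precision on a secondary outcome. The size cannot be fixed from the documents. It is trivial at about 2% missing or less. At an assumed 10% with 986 responders and correlations of 0.4 to 0.7, the variance ratio for multiple imputation is about 0.91 to 0.95, worth about 50 to 83 responders. These figures rest on a linear baseline effect and on baselines missing at random. The power table should not be read as showing the study underpowered: with the planned 1,000 scores, power stays above 80% even at 20% missing.

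**What to change.** In SAP Hypothesis 2, Analysis Plan, replace the exclusion sentence by wording such as: patients without a scored one-year VR-12 are excluded from this model; a missing or partly completed baseline VR-12 is multiply imputed together with Z, assuming missing at random, with arm, randomisation strata, Z, and the 30-day and one-year VR-12 in the imputation model.

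Then:

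- use the same baseline rule in sensitivity analyses 1 and 2, imputing the baseline from observed data before the extreme one-year values are filled in, so that only the outcome assumption changes;
- report the present complete-case exclusion as a sensitivity analysis;
- report the number with a missing baseline by arm.

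Stratum-mean fill with an indicator is not preferred. It gains little or loses precision at correlations above about 0.7, and it can leave a small bias if response depends on arm and baseline together.

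The cost is a few sentences of SAP wording and one imputation step, which should allow for the spline in y0. No new data are needed.
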